4.4.3 Survival Status Follow-Up Phase

Once a patient experiences confirmed disease progression or starts a new anti-cancer therapy, the patient moves into the survival follow-up phase and will be followed up every 12 weeks to determine their disease status. This will be done by reviewing their medical notes and/or contacting the patient or GP directly. Patients will remain on this follow-up until death, withdrawal of consent, or the end of the study, whichever occurs first.

4.5 Study Termination

The 'end-of-trial' is defined as the date when the last patient has completed the 'off-study' visit or the final follow-up visit, whichever is happens last.

4.5.1 Clinical Criteria for Early Trial Termination

Early trial termination will be the result of the criteria specified below:

1. Quality or quantity of data recording is inaccurate or incomplete
2. Poor adherence to protocol and regulatory requirements
3. Incidence or severity of adverse drug reaction in this or other studies indicates a potential health hazard to patients
4. Plans to modify or discontinue the development of the study drug
5. If DLT is seen in Part A in 2 out of 3 or 2 out of 6 patients.

In accordance with the conditions of supply agreement with MSD, ample notification will be provided to the sponsor (via RM-CTU) and sites should alterations to the drug supply change. This is to allow time for appropriate adjustments to be made in regards to the patient's treatment.

4.6 Treatment after End of Study

Following participation in the study patient care will be decided by the local doctor according to standard practice.

5 SELECTION OF PATIENTS

5.1 Screening and Enrolment

The Investigator at the study site will keep a record of all patients screened for entry into this study. Copies of the screening logs will be filed in the Site File. For each patient the primary reason for exclusion will be recorded. Diagnostic data obtained as part of the patient's standard care will be used to determine eligibility provided they fall within the protocol defined timelines. Written informed consent must be obtained prior to the patient undergoing any study specific procedures.

5.2 Registration

When the patient signs the consent form they will be allocated a trial ID that will be used to identify the patient for all future assessments.

Patients can be registered and allocated a trial ID number by contacting the RM-CTU on:

[contact]

[contact]

Email: [contact]

Between Monday to Friday, 9 am to 4 pm.

Once all the screening assessments have been completed and the data entered on the CRFs the patient will be assessed for eligibility. If eligible, the patient will begin on the trial. If the patient is not eligible then the local investigator will make alternative arrangements for the treatment of the patient. The trial ID will be a unique number that once assigned will become the permanent study identifier for that patient. In the event a patient is registered onto the study but does not begin treatment, then that patient's trial ID will not be reassigned. Treatment will begin within 7 days from the date eligibility has been confirmed. To ensure patient confidentiality patients will only be identified on CRFs, other trial specific forms and all communication to RM-CTU using their assigned trial ID. It is the Investigators responsibility to maintain a confidential record of the identity i.e. full name, date of birth and hospital number for the patients enrolled in this study and their assigned trial ID. At the end of the study this record should be archived along with the Site File.

5.3 Patient Replacement Strategy

Additional patients may be enrolled in a given cohort to ensure that the required number of evaluable patients in each cohort is achieved. A patient that discontinues the trial for progressive disease within 3 months of the last dose of radiotherapy will not be evaluable for DLTs and therefore will need to be replaced. A patient that discontinues the trial for a drug-related AE will not be replaced and will be counted in the evaluable population of patients for the respective cohort. However, patients found to have active pneumonitis on C1D1 of pembrolizumab or day 1 of radiotherapy will be removed from the trial and can be replaced. Also patients who

do not reach follow-up 3 months post completion of SBRT for MPM for reasons other than progression or toxicity can be replaced by new patients in that cohort to ensure there is a minimum of 3 (or 6 if required) patients in each cohort.

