4.2 Treatment Regimen

The study will be conducted in two parts; an initial safety phase (Part A), followed by an expansion cohort (Part B). The initial safety phase (Part A) is based on a 3+3 design such that patients will be treated in a cohort of 3-6 patients. A maximum of 6 patients will be allocated to Part A exploring SBRT 30 Gy in 3 fractions in combination with pembrolizumab. If there is more than one DLT in the first 3 patients or two or more DLTs in the first 6 patients, this treatment combination will be deemed as being unacceptable and it would lead to termination of the study. During the expansion cohort (Part B), 12 patients will have SBRT 30 Gy in 3 fractions with pembrolizumab to obtain additional safety and response data. Maintenance pembrolizumab will continue until disease progression, unacceptable toxicities, the patient withdraws consent to the trial, or the patient has completed 35 cycles of treatment. A maximum of 18 patients will be treated in the study.

All patients will receive pembrolizumab on cycle (C) 1 day (D) 1, in Part A and B of the study. All patients will receive SBRT on C1D15, C1D17 and C1D19, as per SBRT protocol (See Appendix 3). Patients in part A will receive SBRT 30 Gy in 3#. Patients in Part B will receive 30 Gy in 3 fractions if considered safe after part A. All patients in Part A and Part B will receive pembrolizumab dosed at 200 mg every 3 weeks, until disease progression, unacceptable toxicities, the patient withdraws consent from the trial or the patient has completed 35 cycles of treatment.

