In the initial safety cohort, a minimum of 3 patients will be treated at the SBRT dose of 30Gy in 3 fractions combined with pembrolizumab. The gap left between the treatments of each subsequent patient will start after the second cycle of Pembrolizumab in the previous dosed patient to mitigate against multiple patients suffering from acute toxicity. The DLT period for this study is 12 weeks from the last dose of SBRT (i.e. at C6D1). Patients included in Part A will be considered by the Safety Review Committee (SRC) once the 3rd and 6th patient in the Part A cohort has completed the DLT period. If 0 out of 3 patients experience a DLT, or if 1 out of 3 patients experience a DLT in Part A, then the cohort will be expanded to 6 patients. If 1 in 6 patients experience a DLT, then it will be acceptable to move forward to the expansion cohort (Part B). However, if ≥ 2 in 6 patients (or more than 1 in the first 3 patients) experience a DLT then the maximum administered dose

(MAD) will have been reached. If the MAD is seen at a dose level of 30 Gy in 3# then the study will be terminated.

While waiting for 3 or 6 patients to complete the DLT period, no additional patients will be recruited. Further patients can only be recruited after the SRC has reviewed the toxicity data for the cohort to proceed to Part B. Patients obtaining complete response or having completed 35 cycles of pembrolizumab must discontinue and may recommence for additional 17 cycles upon subsequent disease, the CI/PI will need to discuss with the sponsor and MSD, on a case by case basis for the continuation of pembrolizumab.

Table 1: SBRT dose level and pembrolizumab dosing during the initial safety cohort and expansion phase.

Dose Level	Pembrolizumab Dose	SBRT to part of a MPM lesion
Initial safety cohort	200 mg i.v. over 30 minutes, every 3 weeks	30 Gy in 3# (Monday, Wednesday, Friday)
Expansion cohort	200 mg i.v. over 30 minutes, every 3 weeks	30 Gy in 3# (Monday, Wednesday, Friday)

SBRT: Stereotactic Ablative Body Radiotherapy; Gy: Gray; i.v.: intravenous; mg: milligrams; #: fraction.

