4.2.1 Dose Limiting Toxicities

Acute toxicity will be assessed up to and including 3 months following the final fraction of radiotherapy (i.e. at C6D1). The MRC dyspnoea score (Appendix 2) will be used to assess dyspnoea at baseline/on treatment and the Common Toxicity Criteria for Adverse Events (CTCAE) version 5.0 will be used to grade all drug and SBRT observed toxicities (Appendix 4). The SRC will consider expansion after the 6th patient in the initial safety cohort has completed the DLT period and reviewed the toxicities before recruitment to the expansion cohort Part B.

Any DLT must be a toxicity that is considered probably, possibly or definitely related to the combination of pembrolizumab and SBRT. DLT is defined as follows:

Haematologic:

- Neutropenia with fever grade 3 or neutropenia grade 4
- Thrombocytopenia with bleeding grade 3 or thrombocytopenia grade 4

Non-Haematologic:

Any ≥ 3 non-haematological toxicity which is definitely, probably or possibly related to the combination of pembrolizumab and SBRT for pleural mesothelioma including the following:

- Increased MRC dyspnoea score > 2 grades from baseline and/or acute dyspnoea grade ≥ 4 (or CTCAE dyspnoea grade ≥ 3) persisting for > 7 days (including weekend).
- Pneumonitis grade ≥ 3 persisting for > 7 days (including weekend).
- Oesophagitis grade ≥ 3 persisting for > 7 days (including weekend).
- Toxicity leading to interruption of radiotherapy for > 7 days (including weekend).

Progression of the study will not proceed until the following criteria are satisfied by the SRC:

- If 0 out of 3 patients experience a DLT, or if 1 out of 3 patients experience a DLT, a further 3 patients will be recruited at the dose level in the initial safety cohort.
 - If 0 out of 6 patients experience a DLT, or if 1 out of 6 patients experience a DLT, then progression to Part B of the study can proceed.
 - If ≥ 2 out of 6 patients (or more than 1 in the first 3 patients) experience a DLT, then there will be no Part B expansion phase and the study will be terminated.

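### Section 5.3 can drop a recorded DLT from the Part A count if the patient later leaves for progression, and one treated replacement on the way to a full Part B breaks the stated maxima of 6 and 18

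*Protocol*

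**What the plan says.** **Who is evaluable (5.3).** "A patient that discontinues the trial for progressive disease within 3 months of the last dose of radiotherapy will not be evaluable for DLTs"; the sentence goes on to require replacement. The only patients expressly kept are defined by their reason for leaving: "A patient that discontinues the trial for a drug-related AE will not be replaced and will be counted in the evaluable population" of the cohort. Nothing is said about a patient who has a DLT, stays on trial and later leaves for progression. Extra patients may be enrolled to reach the evaluable number, with no ceiling.

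**When the trial stops (4.2, 4.2.1, 4.5.1).** Section 4.2 makes the combination unacceptable "If there is more than one DLT in the first 3 patients or two or more DLTs in the first 6 patients". Section 4.2.1 repeats the thresholds: if 2 or more of 6, or more than 1 of the first 3, "experience a DLT, then there will be no Part B expansion phase and the study will be terminated". Section 4.5.1 lists as a termination criterion: "If DLT is seen in Part A in 2 out of 3 or 2 out of 6 patients". None of these restricts the count to evaluable patients.

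**How many patients (1, 4.2, 9.2).** Part A is limited to 6, Part B adds 12, and the trial is limited to 18 recruited (section 1) or treated (section 4.2).

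**The window.** Section 4.2 sets the DLT period at 12 weeks after the last SBRT dose. Section 4.2.1 assesses acute toxicity to 3 months after the final fraction. Both tie this to C6D1. Section 5.3 uses 3 months with no visit named.

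**The concern.** The DLT count in Part A decides whether Part B opens, and the DLT proportion is the primary endpoint (9.1.1). Section 5.3 classifies a patient by the reason for leaving and not by whether a DLT occurred, so an observed DLT can fall out of the formal count when the recorded reason is progression. The termination rules, read as written, would still count it. The protocol does not say which prevails, so the Safety Review Committee could face a mandatory stop under one section and an instruction to replace the patient and continue under another.

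The maxima are a second and simpler conflict. Uncapped replacement cannot coexist with fixed limits of 6 and 18 patients once anyone treated in Part A is replaced.

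**Working it through.** **1. Can the case arise?** Section 4.2.1 makes related non-haematological toxicity of grade 3 or above a DLT. Table 8 permanently stops pembrolizumab for many such events (grade 3-4 pneumonitis, renal events, and AST, ALT or bilirubin rises, with an exception for some patients with liver metastases). Patients who leave for those are kept by 5.3. Table 8 only holds treatment for grade 3 colitis, grade 3 skin reactions and most other grade 3 toxicity, so such a patient can stay on trial and later leave for progression. The first 9-week CT falls at about day 64 (C4D1 = 3 × 21 + 1). Stable patients are confirmed no sooner than 28 days later, day 92 (6.3.11.4). Clinically unstable patients need no confirmatory scan (6.3.11.3). The window ends at about day 103 (19 + 84). The case is possible but narrow.

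**2. The count, with no assumed rates.** Two DLTs, one of those patients held and later out for progression:

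| | 4.2, 4.2.1, 4.5.1 | 5.3 read literally | 5.3 after a DLT-free replacement |
|---|---|---|---|
| First three | 2/3, stop | 1/2, no decision | 1/3, expand to 6 |
| First six | 2/6, stop | 1/5, no decision | 1/6, go |

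If 9.1.1 used the 5.3 population, the primary proportion would be 1/6 = 17% (exact 95% CI 0.4% to 64%) instead of 2/6 = 33% (4% to 78%).

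**3. The maxima.** 6 + 12 = 18 reproduces the stated figure, with no replacements. One treated replacement in Part A gives 7, and 7 + 12 = 19. Part B opens only after six evaluable patients, so this follows whenever a treated Part A patient is replaced and Part B then recruits its 12. It does not need the narrow overlap in step 1.

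**4. Illustration only.** Let p be the DLT rate, d the chance of leaving for progression in the window, and f the share of DLTs that lead only to a hold. All three are assumptions. DLT and progression are taken as independent, with the DLT first. The probability that a counted patient has a DLT is

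- literal 5.3: q = p(1 − fd) / [p(1 − fd) + (1 − p)(1 − d)]
- recorded DLT always counted: q = p / [p + (1 − p)(1 − d)]

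and P(go) = (1 − q)^6 + 6q(1 − q)^5. With p = 0.30 and f = 0.5:

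| d | literal q | P(go) | always-counted q | P(go) | gap |
|---|---|---|---|---|---|
| 5% | 0.306 | 0.408 | 0.311 | 0.397 | 0.011 |
| 10% | 0.312 | 0.396 | 0.323 | 0.373 | 0.023 |
| 24% | 0.332 | 0.354 | 0.361 | 0.300 | 0.055 |
| 40% | 0.364 | 0.294 | 0.417 | 0.208 | 0.086 |

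At d = 24% the gap is 0.026 if f = 0.25 and 0.121 (0.420 v 0.300) if f = 1. The 24% is simply 100% − 76%, from the disease control rate quoted in 2.2.6.2. It is not an estimate of early exit in this trial.

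**5. The window.** From the last fraction on day 19, 12 weeks is day 103. C6D1 is 5 × 21 + 1 = day 106, or days 103 to 109 with the ±3-day visit allowance in Table 3. Three calendar months (89 to 92 days) is days 108 to 111.

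**The case against.** The stop rule is clear and stated more than once, and it turns on patients who experience a DLT. Section 5.3 is about replacement: its purpose is to reach enough evaluable patients, and its other clauses lean towards keeping toxicity cases (drug-related exits are retained, and its last clause does not allow replacement of patients lost through toxicity). On that reading early progressors are non-evaluable because they were not observed long enough, and nobody intended to discard a DLT. The Safety Review Committee sees all SAEs (11.9), and 9.1.1 tabulates all toxicities. Much of this stands: it is probably what was meant. But the progression sentence is unqualified and replacement is required, so the intended reading has to be supplied by the reader.

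Four stronger readings are tempting and are not supported:

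- *The same six patients give both stop and go.* They give 2/6 or 1/5. Go needs a seventh, DLT-free patient.
- *Section 5.3 biases the DLT rate downwards.* Under independence it does not: at p = 0.30 and d = 24% the counted rate is 30% if every DLT is only held and 33% if half are.
- *Section 5.3 overrides the stop rule, or a DLT goes unseen.* The rule stands and the event is still reported. What is missing is a statement of which text governs the count.
- *The 12-week and 3-month wordings are a substantive defect.* Sections 4.2 and 4.2.1 both point to C6D1, and the dates differ by about a week. This is a tidy-up.

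**Conclusion.** The point holds in a limited form. As written, 5.3 can remove an observed DLT from the count on which 4.2, 4.2.1 and 4.5.1 terminate the trial, in the narrow case of a DLT managed by a hold and followed by exit for progression inside the window. There, 2/6 (stop) becomes 1/5, and 1/6 (go) if the required replacement is DLT-free. That rests on the text alone. How often it would happen cannot be estimated from the documents. With half of DLTs only held and a 30% DLT rate, the effect on P(go) is about 1 to 5 percentage points for early progression of 5% to 24%, entirely under assumed rates. The effect on the primary proportion is conditional, because 9.1.1 does not name its denominator and the analysis plan may.

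The conflict over maxima is firmer: a single treated Part A replacement, followed by a full Part B, gives 7 and 19 against 6 and 18. It would not arise if the replaced patient was never treated (for the limit on patients treated), if the trial stopped at the first look, or if Part B fell short of 12.

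**What to change.** - Define DLT-evaluable once: a patient who has a DLT in the DLT window or completes the window.
- State in 5.3 that a patient with a recorded DLT is always counted and not replaced, and that only DLT-free patients who do not complete the window may be replaced.
- Use this population in 4.2, 4.2.1, 4.5.1, 9.1.1 and the review trigger in 9.1.4, and also report DLTs over all Part A patients who received SBRT.
- Restate 6 and 18 as evaluable patients, with a separate maximum treated in Part A and overall.
- As a minor tidy-up, reconcile the 12-week, 3-month and C6D1 wording across 4.2, 4.2.1 and 5.3.

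**Cost.** Wording, plus one decision on the maximum treated. The counted DLT proportion becomes slightly less favourable, because DLT-free early progressors are still replaced while DLT patients are not. Under the illustrative assumptions (30% DLT rate, 24% early progression, half held) it is 36% instead of 33%. At a true 20% DLT rate with the same d and f, P(go) falls from 60% to 54%. Reporting the proportion over all patients who received SBRT makes that tilt visible.

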5.4 Entry Criteria

The following eligibility criteria were designed to select patients for whom the protocol treatment is considered appropriate. All relevant medical and non-medical conditions should be taken into consideration when deciding whether this protocol is suitable for a particular patient. Eligibility criteria may not be waived by the investigator.

5.4.1 Inclusion criteria

In order to be eligible for participation in this trial, the patient must:

1. Patients should be ≥ 18 years old on the day of signing the informed consent.
2. Patients must have a histological or cytological diagnosis of MPM.
3. Patients should have non-radically treatable MPM (i.e. not being considered for extrapleural pneumonectomy or pleurectomy and decortication).
4. Patients must have measurable disease as assessed by mRECIST (i.e. at least a 1 cm rind of MPM at 2 sites on 3 different levels).
5. Patients must have had disease progression or be intolerant of standard first-line palliative chemotherapy for MPM. Patients who have declined first-line palliative chemotherapy must have been suitable for platinum-doublet combination chemotherapy.
6. Patient should have an ECOG performance status 0-1.
7. Patients should be able to tolerate a course of stereotactic radiotherapy as assessed by the investigator.
8. Patients should have pleural based disease, away from critical structures, and suitable for treatment to part of lesion with SBRT for pleural mesothelioma.
9. Patients must have adequate organ function including MRC dyspnoea score < 3 and adequate baseline lung function tests, with an $FEV_1 > 0.8L$ or $> 30\%$ of predicted and a $TLCO > 30\%$.
10. Demonstrate adequate organ function as detailed in Table 2 (based on bloods within 10 days of C1D1).
11. Have provided tissue from an archival tissue sample or newly obtained tissue sample.
- 12.
13. Female patient of childbearing potential should have a negative serum pregnancy within 72 hours prior to receiving the first dose of study medication (C1D1). Female patients of childbearing potential should be willing to use highly effective methods of contraception for the course of the study through 120 days after the last dose of study medication. Female of childbearing potential is defined as women following menarche and until becoming post-menopausal unless permanently sterile. Permanent sterilisation

methods include hysterectomy, bilateral salpingectomy and bilateral oophorectomy. A postmenopausal state is defined as no menses for 12 months without an alternative medical cause.

14. Male patients should agree to use an adequate method of contraception starting with the first dose of study therapy through 120 days after the last dose of study therapy.
15. Be willing to provide informed consent for the trial.

Table 2: Adequate Organ Function Laboratory Values

System	Laboratory Value
Haematological	
• Absolute neutrophil count (ANC)	$\geq 1.5 \times 10^9/L$
• Platelets	$100 \times 10^9/L$
• Haemoglobin	$\geq 90 \text{ g/L}$ or $\geq 5.6 \text{ mmol/L}$
Renal	
• Serum creatinine OR	$\leq 1.5 \times$ upper limit of normal (ULN) OR
• Measured or calculated ^a creatinine clearance	$\geq 60 \text{ mL/min}$ for patient with creatinine levels $> 1.5 \times$ institutional ULN
^a Creatinine clearance should be calculated per institutional standard.	
Hepatic	
• Serum total bilirubin OR	$\leq 1.5 \times$ ULN OR \leq ULN for patients with total bilirubin levels $> 1.5 \times$ ULN
• Direct bilirubin	
• AST (SGOT) and ALT (SGPT)	$\leq 3 \times$ ULN OR $\leq 5 \times$ ULN for patients with liver metastases
Coagulation	
Prothrombin Time (PT)	$\leq 1.5 \times$ ULN unless patient is receiving anticoagulant therapy as long as PT or PTT is within therapeutic range of intended use of anticoagulants
Activated Partial Thromboplastin Time (aPTT)	$\leq 1.5 \times$ ULN unless patient is receiving anticoagulant therapy as long as PT or PTT is within therapeutic range of intended use of anticoagulants

5.4.2 Exclusion Criteria

The following patients must be excluded from participating in the trial:

1. Patients who have taken any investigational medicinal product or have used an investigational device within 4 weeks of the first dose of pembrolizumab. Patients are allowed to participate in additional observational studies.
2. Patients who have received prior chemotherapy, targeted small molecule therapy or radiotherapy within 4 weeks prior to the first dose of pembrolizumab.

3. Patients with a diagnosis of immunodeficiency or be receiving systemic steroid therapy (>7.5 mg of prednisone / >1 mg of dexamethasone or their equivalent dose) or any other form of immunosuppressive therapy within 7 days prior to the first dose.
4. Patients with evidence of active autoimmune disease requiring systemic treatment within the past 3 months or a documented history of clinically severe autoimmune disease, or a syndrome that requires systemic steroids or immunosuppressive agents or an autoimmune disease that is currently quiescent off any treatment, but deemed at risk of a significant flare if treated on this protocol.
5. Patients who have received prior therapy with an anti-PD-1, anti-PD-L1, anti-PD-L2, anti-CD137, or anti-Cytotoxic T-lymphocyte-associated antigen-4 (CTLA-4) antibody (including ipilimumab or any other antibody or drug specifically targeting T-cell co-stimulation or checkpoint pathways).
6. Patients with evidence of active central nervous system (CNS) metastases and/or carcinomatous meningitis. Patients with previously treated brain metastases may participate provided the brain metastases are stable and there is no evidence of new or enlarging brain metastases.
7. Patients who have had previous radiotherapy to the thorax or other neighbouring region that would preclude the safe administration of SBRT for MPM.
8. Patients with evidence of interstitial lung disease or active, non-infectious pneumonitis.
9. Patients with evidence of additional malignancy that is progressing or requires active treatment.
10. Patients with a history or current evidence of any condition, therapy, or laboratory abnormality that might confound trial results, interfere with the patient's participation or is not in the best interest of the patient.
11. Patients with psychiatric or substance abuse disorders that would interfere with patients participation.
12. Patients who are pregnant / breastfeeding or expecting to conceive within the duration of the trial, starting with the screening visit through 120 days after the last dose.
13. Patients with a history of HIV, HIV 1/2 antibodies, Hepatitis B or Hepatitis C.
14. Patients with any active infection requiring systemic treatment
15. Patients who have received a live vaccine within 30 days prior to the first dose of trial treatment.
16. Patients with known hypersensitivity to the active substance pembrolizumab or to any of the excipients listed in the IB.

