Summary of Main Exclusion Criteria	
 1. Patients who have taken any investigational medicinal product or have used an investigational device within 4 weeks of the first dose of pembrolizumab. Patients are allowed to participate in additional observational studies. 2. Patients who have received prior chemotherapy, targeted small molecule therapy or radiotherapy within 4 weeks prior to the first dose of pembrolizumab. 3. Patients with a diagnosis of immunodeficiency or be receiving systemic steroid therapy (>7.5 mg of prednisone / >1 mg of dexamethasone or their equivalent dose) or any other form of immunosuppressive therapy within 7 days prior to the first dose. 4. Patients with evidence of active autoimmune disease requiring systemic treatment within the past 3 months or a documented history of clinically severe autoimmune disease, or a syndrome that requires systemic steroids or immunosuppressive agents or an autoimmune disease that is currently quiescent off any treatment, but deemed at risk of a significant flare if treated on this protocol. 5. Patients who have received prior therapy with an anti-PD-1, anti-PD-L1, anti-PD-L2, anti-CD137, or anti-Cytotoxic T-lymphocyte-associated antigen-4 (CTLA-4) antibody (including ipilimumab or any other antibody or drug specifically targeting T-cell co-stimulation or checkpoint pathways). 6. Patients with evidence of active central nervous system (CNS) metastases and/or carcinomatous meningitis. Patients with previously treated brain metastases may participate provided the brain metastases are stable and there is no evidence of new or enlarging brain metastases. 7. Patients who have had previous radiotherapy to the thorax or other neighbouring region that would preclude the safe administration of SBRT for MPM. 8. Patients with evidence of interstitial lung disease, or history of pneumonitis (including non-infectious pneumonitis) that required steroids, or current pneumonitis (including non-infectious pneumonitis). 9. Patients with evidence of additional malignancy that is progressing or requires active treatment. 10. Patients with a history or current evidence of any condition, therapy, or laboratory abnormality that might confound trial results, interfere with the patient's participation or is not in the best interest of the patient. 11. Patients with psychiatric or substance abuse disorders that would interfere with patients participation. 12. Patients who are pregnant / breastfeeding or expecting to conceive within the duration of the trial, starting with the screening visit through 120 days after the last dose. 13. Patients with a history of HIV, HIV 1/2 antibodies, Hepatitis B or Hepatitis C. 14. Patients with any active infection requiring systemic treatment 15. Patients who have received a live vaccine within 30 days prior to the first dose of trial treatment. 16. Patients with known hypersensitivity to the active substance pembrolizumab or to any of the excipients listed in the IB.

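### The exclusion list in section 5.4.2 drops the history of steroid-treated pneumonitis that the Trial Summary excludes

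*Protocol*

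**What the plan says.** Item 8 of the main exclusion criteria in the Trial Summary (section 1) has three limbs: interstitial lung disease, past pneumonitis that needed steroids, and current pneumonitis. The second and third read "history of pneumonitis (including non-infectious pneumonitis) that required steroids, or current pneumonitis", with non-infectious disease expressly included in each.

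Item 8 in section 5.4.2, under the lead-in "The following patients must be excluded from participating in the trial", reads "Patients with evidence of interstitial lung disease or active, non-infectious pneumonitis". It has no history limb, and it limits current pneumonitis to the non-infectious kind.

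Section 5.4 adds that the investigator may not waive eligibility criteria. Section 5.3 provides that "patients found to have active pneumonitis on C1D1 of pembrolizumab or day 1 of radiotherapy will be removed from the trial" and can be replaced. Section 4.2.1 lists grade 3 or higher pneumonitis persisting for more than 7 days among the DLTs. Under sections 4.2 and 4.2.1 the study is terminated if two or more of the six Part A patients, or more than one of the first three, have a DLT.

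**The concern.** Section 5.4.2 is the list that opens with a mandatory instruction, so a site would be expected to screen from it. Applied item by item, it does not expressly exclude a patient who has recovered from steroid-treated pneumonitis, although the Summary does. Such a patient could receive pembrolizumab plus thoracic SBRT in a trial that treats pneumonitis as a principal hazard. Besides the DLT definition, the schedule in section 6.1 adds chest x-rays to monitor for pneumonitis and a high-resolution CT before cycle 2.

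Two things are at stake. The first is the safety of that patient, which does not depend on any calculation. The second is the population behind the Part A decision. With six patients and a stopping threshold of two, one patient with a different underlying risk matters, and two sites reading different pages could enrol different populations.

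**Working it through.** **1. The two texts side by side**

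| Situation | Trial Summary, item 8 | Section 5.4.2, item 8 |
|---|---|---|
| Interstitial lung disease | excluded | excluded |
| Past pneumonitis that required steroids, now resolved | excluded | not mentioned |
| Current non-infectious pneumonitis | excluded | excluded |
| Current infectious pneumonitis | excluded | not mentioned |

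The other 15 items match between the lists. Abbreviation does not explain the difference, because here the summary is stricter than the full list.

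**2. Does another provision close the history gap?**

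- Exclusion 2 bars chemotherapy, targeted therapy or radiotherapy only within 4 weeks of the first dose.
- Exclusion 3 looks back only 7 days for steroids.
- Exclusion 4 concerns autoimmune disease, or a syndrome that currently requires steroids or immunosuppression.
- Exclusion 5 removes everyone with prior checkpoint-inhibitor therapy, but not pneumonitis from other causes.
- Exclusion 7 applies only if earlier thoracic radiotherapy precludes safe SBRT.
- Exclusion 10, which opens "Patients with a history or current evidence of any condition, therapy, or laboratory abnormality that might confound trial results", could be used, but it is a matter of judgement. So is inclusion 7 (ability to tolerate SBRT).
- Inclusion 9 (lung function and dyspnoea score) measures current function, not history.
- Section 5.3 concerns active pneumonitis only.

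None is an express bar. The gap on infectious pneumonitis is minor: exclusion 14, "Patients with any active infection requiring systemic treatment", and the removal rule in 5.3 largely cover it.

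**3. Sensitivity of the Part A decision**

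The Protocol gives no DLT rate and no expected number of such patients, so there is no figure to reproduce and what follows is a range of assumptions. The design input is that the study proceeds only with at most one DLT in six. The rule of more than one DLT in the first three is contained in this.

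Let *b* be the DLT risk of an ordinary patient, *h* = 1.5*b* or 2*b* the risk of a patient with the history, and *k* the number of such patients among six, with independent outcomes:

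P(stop) = 1 − P(0 DLTs) − P(1 DLT), where

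P(0) = (1−h)^k (1−b)^(6−k)

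P(1) = k·h·(1−h)^(k−1)·(1−b)^(6−k) + (6−k)·b·(1−h)^k·(1−b)^(5−k)

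Example with *b* = 0.20:

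- *k* = 0: P(0) = 0.8^6 = 0.262; P(1) = 6 × 0.2 × 0.8^5 = 0.393; P(stop) = 0.345.
- *k* = 1, *h* = 0.40: P(0) = 0.6 × 0.8^5 = 0.197; P(1) = 0.4 × 0.8^5 + 5 × 0.2 × 0.6 × 0.8^4 = 0.131 + 0.246 = 0.377; P(stop) = 0.427 (from unrounded terms).

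| Assumed *b* | No such patient | One, at 1.5*b* to 2*b* | Two, at 1.5*b* to 2*b* |
|---|---|---|---|
| 10% | 11.4% | 13.1–14.7% | 14.8–18.4% |
| 20% | 34.5% | 38.6–42.7% | 42.7–50.8% |
| 30% | 58.0% | 63.4–68.8% | 68.4–78.0% |

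The shift is about 2 to 11 percentage points with one such patient and 3 to 20 with two. The direction is towards stopping more often, not towards unsafe progression to Part B.

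**The case against.** The wording difference is not disputable; its weight is. Exclusion 5 removes all checkpoint-inhibitor pneumonitis, exclusion 7 some prior thoracic radiotherapy, item 8 itself interstitial lung disease, and inclusion 9 poor lung function. What remains is mainly resolved pneumonitis from another cause in a patient with acceptable function, and the Protocol gives no count of these. Section 5.4 also asks that all relevant conditions be considered, and exclusion 10 stands under the same mandatory heading and refers to history and to the patient's best interest. A careful investigator could exclude the patient on that basis, or comply with both texts by applying the stricter one.

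This stands as far as it goes: it makes enrolment of such a patient less likely. It does not remove the contradiction, because two investigators may use a judgement clause differently. If exclusion 10 were sufficient, the Summary's specific history limb would be redundant.

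The objection to the stopping probabilities also has force. They multiply the whole DLT risk, whereas a pneumonitis history would plausibly raise mainly the pulmonary part. Suppose, again as an assumption, that pneumonitis makes up a quarter of a 20% risk and only that part doubles. The patient's risk is then 0.15 + 2 × 0.05 = 0.25, and P(stop) = 1 − 0.75 × 0.8^5 − (0.25 × 0.8^5 + 5 × 0.2 × 0.75 × 0.8^4) = 36.5%, against 42.7% with the whole risk doubled. The table is best read as an illustration near the upper end.

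**Conclusion.** The concern holds as an internal contradiction in a safety criterion. Two current passages give different populations, no rule of precedence exists, and no other criterion expressly bars a patient with resolved, steroid-treated pneumonitis. It should be corrected because that patient would receive a combination for which severe pneumonitis is a named DLT.

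The effect on Part A is secondary and cannot be fixed from the Protocol. It depends on an assumed base risk of 10% to 30%, a risk ratio of 1.5 to 2 applied to all DLTs, and one or two such patients in six. It would be smaller if only the pulmonary risk rises. The Protocol does not show which version is intended. The stricter one is the safer default.

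**What to change.** Replace item 8 of section 5.4.2 with item 8 of the Trial Summary in full, so that it covers interstitial lung disease, past pneumonitis that required steroids, and current pneumonitis, each including non-infectious disease. Only if the sponsor has a documented reason for the narrower criterion should the Summary be changed to match instead.

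Align the eligibility page of the case report form with the chosen text, and check which version was applied to any patient already screened.

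The cost is a one-line amendment, a form check, a review of any screened patients, and possibly a few fewer eligible patients. Medical history is already collected at screening (section 6.2.3), so no new assessment is needed.
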